At week 4 and 6 patients will undergo 30% salicylic acid peels and be asked to report any adverse events. In addition, the study investigator will take mexameter readings from the peeled/unpeeled sides and calculate a MASI score on both the peeled/unpeeled sides at week 4 (investigator will be blinded as to which side was peeled). At weeks 8 and 14, patients will report any adverse events and the study investigator will take mexameter readings and calculate a MASI score as above. The physician will also perform a melasma severity assessment for each side of the face at weeks 8 and 14. In addition, at 8 and 14 weeks, both the physician and patient will perform a subjective global evaluation of which side, if any, had more improvement in the following terms: no change/slight/moderate/marked.

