### Treatment Assignment, Blinding, and Randomization

Patients will all be given 4% hydroquinone to use on the affected areas for 14 weeks. In addition, each patient will receive biweekly salicylic acid peels to half of the face for a total of four peels (at week 0, 2, 4, 6). The first two peels will be 20% salicylic acid and the last two peels will be 30% salicylic acid. The side to be peeled will be determined by a computer generated randomization code. Only the investigators will be blinded in the study, due to the

nature of the treatments it will not be possible for the patients or the nurse performing the peels to be blinded.

No concomitant therapy will be allowed for the duration of the study. Patients who were already on an oral contraceptive pill will be allowed to continue the pills during the study, but oral contraceptive pills may not be introduced during the study.

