## **8 Evaluation Criteria**

Patients satisfying inclusion criteria will be chosen to participate in the study. The degree of pigmentation will be noted at baseline by mexameter readings taken on both sides of the face on affected skin and also nearby normal skin. Additional mexameter readings will be taken at weeks 2, 4, 8, and 14. In addition standard and polarized photographs will be taken at baseline and at weeks 8 and 14. A MASI score will also be calculated at baseline and at weeks 2, 4, 8, and 14. A melasma severity assessment will be performed by the physician at baseline and at weeks 8 and 14. A physician and patient global assessment will be performed at weeks 8 and 14, a subjective measure of which side, if any, improved more and to what degree (no change/slight/moderate/marked). Primary efficacy assessment will be improvement of melasma using mexameter readings while secondary assessment will be improvement in MASI scores, melasma severity assessment, and physician and patient global improvement compared with the opposite side.

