## **11 Statistical Considerations**

Investigators will enter the information required by the protocol into the Study Report Forms (SRFs). Additionally, a series of standardized photographs will be taken of each patient at baseline and 14 weeks to provide permanent documentation.

The objective of this trial is to study the efficacy and tolerability of salicylic acid peels in the treatment of melasma in Hispanic women. The data will be summarized with respect to efficacy and safety observations. Data will be presented for the complete intent-to-treat population (all patients having taken at least one dose of study medication) as well as the per-protocol population (all patients who completed the study without major protocol deviations).

The assessment of safety will be based mainly on the frequency of adverse events, which includes all serious adverse events. Adverse events will be summarized by presenting for each treatment group the number and percentage of patients having any adverse event, having an adverse event in each body system, and having each individual adverse event. Any other information collected (e.g. severity or relatedness to study medication) will be listed as appropriate.

Efficacy will be primarily assessed by comparing delta mexameter readings (affected skin-nearby normal skin) on the peeled versus unpeeled side. This data will be analyzed using a two factor repeated measures analysis of variance. Efficacy will be secondarily assessed by change in MASI score on the peeled versus unpeeled side also using the repeated measures analysis of variance. Another secondary measure of efficacy will be the melasma severity assessment of the peeled versus unpeeled side also using the repeated measures analysis of variance.

A McNemar chi-squared test will be used to determine if there is agreement between the Physician and Patient Global Assessment of Improvement at 8 and 14 weeks as to which side appears more improved. For those in which there is agreement, we will further look at the degree of agreement and use the McNemar chi-squared test to see how well they correlate. The critical value for all efficacy, tolerability, and subject satisfaction survey analyses will be 0.05.

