A previous study has shown that using 4% hydroquinone cream alone results in total improvement in melasma in ~40% of patients (4). However, the assessments of melasma improvement were more subjective than objective in nature and differ from the end points we are using in our study. Furthermore, it is unclear how much more improvement we may see with the addition of the salicylic acid peels. Since we do not know how much improvement to expect given our efficacy endpoints, we will be performing a pilot study recruiting ~20 patients.

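### Degree of improvement is compared only in pairs that already agree on side, so the result cannot show overall physician-patient agreement and turns on an unstated rule for neither-side ratings

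*Combined protocol and SAP*

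**What the plan says.** Section 6 has two raters make the same judgement at weeks 8 and 14: "both the physician and patient will perform a subjective global evaluation of which side, if any, had more improvement". Section 8 describes this as "a subjective measure of which side, if any, improved more and to what degree (no change/slight/moderate/marked" and lists physician and patient global improvement among the secondary assessments. Each rater therefore supplies a side (peeled, unpeeled or neither) and a degree on four levels.

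Section 11 analyses the pair of ratings in two steps:

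- **Side**, at both rating visits: "A McNemar chi-squared test will be used to determine if there is agreement between the Physician and Patient Global Assessment of Improvement at 8 and" (the sentence goes on to name the later visit).
- **Degree.** "For those in which there is agreement, we will further look at the degree of agreement". The plan will then "use the McNemar chi-squared test to see how well they correlate".

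Section 11 gives no degree analysis for pairs that disagree on side. It does not say whether two neither-side ratings count as agreement, whether the degree score carries the side, or how a four-level scale enters a McNemar test. It plans no correlation coefficient or kappa.

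Two facts give the context. On blinding, "Only the investigators will be blinded in the study", so the patient knows which side was peeled. On size, "we will be performing a pilot study recruiting ~20 patients".

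**The concern.** Side and degree are two parts of one judgement. If degree is examined only after agreement on side, patients are selected on part of the quantity being measured. A physician who rates the peeled side markedly better and a patient who rates the unpeeled side markedly better are as far apart as the scale allows, yet that pair is absent from the degree result. If two neither-side ratings count as agreement, the opposite happens: both degrees are no change by construction, and the pair adds a forced match.

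The comparison sets a blinded rater beside an unblinded one. Readers will use it to judge whether the patient's impression is corroborated. A figure that leaves out the clearest contrary evidence, and that moves with an unstated scoring rule, does not answer that question.

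**Working it through.** The documents state no agreement rate or correlation, so there is no planned figure to reproduce. The rates below are assumptions.

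**1. Does the side step cover the omitted pairs?** McNemar uses the two discordant counts, b and c: chi-squared = (b - c)² / (b + c).

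- Suppose all 20 pairs name opposite sides, split b = 10 and c = 10. Chi-squared = 0 and exact p = 1.0, although no pair agrees.
- Suppose two raters rank patients identically on degree but one rates higher, giving b = 8 and c = 0. Exact p = 2 × 0.5⁸ = 0.008, although the rank correlation is perfect.

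The test compares margins. It does not measure agreement or correlation.

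**2. Hand calculation for unrelated raters.** Assume that peeled, unpeeled and neither are equally likely, and that slight, moderate and marked (scored 1, 2, 3) are equally likely.

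- Same side named: 2/9. Both neither: 1/9. Agreeing subset: 3/9, of which 1/3 are forced no-change pairs.
- Exact match in the subset: 1/3 + (2/3)(1/3) = 0.56. In all patients: 1/9 + (2/9)(1/3) = 0.185.
- Let p be the share of the subset that names a side. The unsigned degrees have covariance 4p - 4p² and variance 14p/3 - 4p², so r = 4(1 - p) / (14/3 - 4p). With p = 2/3, r = 1.333 / 2.000 = 0.67.
- Without the joint neither-side pairs, p = 1 and r = 0.

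**3. How this depends on the neither-side rate.** Unrelated raters, joint neither-side pairs kept, unsigned degree. The ranges cover the peeled side being chosen 50%, 70% or 90% of the time and degree splits of 1:1:1 or 3:2:1.

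| Neither-side rate | Subset r | Subset kappa |
|---|---|---|
| 0.1 | 0.07-0.13 | 0.03-0.05 |
| 0.2 | 0.26-0.40 | 0.12-0.20 |
| 1/3 | 0.54-0.67 | 0.32-0.43 |
| 0.5 | 0.73-0.80 | 0.52-0.60 |

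With those pairs dropped, r and kappa are 0.00 in every scenario. If the score carries the side, same-side pairs from unrelated raters give r of 0.83-0.86 when sides are chosen 50:50, 0.72-0.76 at 70:30 and 0.19-0.22 at 90:10.

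**4. Raters who are related.** Two latent normal ratings with mean 0 are cut at ±0.43, ±0.97 and ±1.38 into scores from -3 to +3, so about 1/3 of ratings are neither side.

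| Latent correlation | All patients, signed r | Subset, joint neither-side kept | Subset, joint neither-side dropped |
|---|---|---|---|
| 0 | 0.00 | 0.60 | 0.00 |
| 0.3 | 0.28 | 0.60 | 0.08 |
| 0.5 | 0.47 | 0.63 | 0.17 |
| 0.7 | 0.66 | 0.69 | 0.30 |

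With those pairs kept, the subset figure hardly moves as true agreement goes from none to good. With them dropped, it understates agreement because the range is restricted. With a peel effect of 0.5 latent SD and unrelated raters, the two subset values are 0.53 and 0.02.

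**5. Patients outside the degree step.** With joint neither-side pairs kept, 38% to 67% are outside across these latent scenarios, or about 8 to 13 of 20. With them dropped, the equal-rates case in step 2 leaves out 1 - 2/9 = 78%, or about 16 of 20.

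**6. Effect on the planned test.** Unrelated raters, N = 20, degree cut at moderate or more (probability 2/3 for each rater), 20,000 runs. McNemar is non-significant in 95-97% of runs in the agreeing subset (mean 6.4 to 13.3 patients) and in 96% with all 20 patients.

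**The case against.** A two-step analysis, side first and then degree given side, is a recognisable conditional question. Section 11 frames the first step as agreement on which side looks better, so a pair naming no side need not count as agreement. On that reading, unrelated raters show no spurious correlation. This stands. A reader might infer that unrelated raters would always appear strongly correlated under this plan. The documents do not support that: it requires joint neither-side pairs to be kept and common, or a score that carries the side with both sides often chosen.

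A reader might also infer that patients who disagree are dropped altogether. They are not. Both raters score them at weeks 8 and 14, and they belong to the side step. They are missing only from the degree step. Even so, the side step does not measure their disagreement, as the 10/10 split shows.

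Third, the planned statistic is McNemar, and step 6 shows that the restriction hardly alters its result. Under the written plan, a false appearance of agreement would come mainly from the choice of test. This also stands. It does not make the subset harmless, because a correlation or kappa put in McNemar's place but confined to the same subset would inherit the behaviour in step 4.

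Last, the stakes are low. The primary outcome is the mexameter reading, this analysis estimates no treatment effect, and the documents attach no decision to it. I accept that as setting the priority.

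**Conclusion.** The point holds in limited form. Section 11 restricts the degree comparison to pairs agreeing on side, and neither step then measures opposite-side disagreement. Under neither reading of agreement does the subset figure recover the overall correlation. With about 1/3 of ratings neither side, unrelated raters give about 0.60 or 0.00 depending on a rule the plan does not state. Under the second reading, raters with latent correlation 0.7 give about 0.30, against 0.66 in all patients.

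These sizes rest on assumed rates and a latent-normal model. At a neither-side rate of 0.1 the inflation for unsigned degree is only 0.07-0.13. The documents do not support a claim that the planned McNemar p-value is materially distorted by the restriction. Priority is minor.

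**What to change.** In Section 11, replace the sentence that opens the degree step with the following plan:

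- Combine side and degree into one signed score per rater: -3 for unpeeled side marked, 0 for neither side, +3 for peeled side marked. Derive it from the randomisation code after the blinded physician has rated, so that blinding is kept.
- Compare physician and patient scores in all rated patients, separately at weeks 8 and 14, with one chance-corrected agreement statistic such as weighted kappa. State the weights in advance and give the confidence interval.
- Show the full physician-by-patient cross-table, including opposite-side and neither-side pairs.
- Show degree agreement among same-side pairs only as a labelled descriptive supplement, saying how joint neither-side pairs are handled.

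With all patients kept on the signed scale, unrelated raters give r = 0.00 in every scenario of step 3.

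The cost is wording only, since side and degree are already collected from both raters. The downsides are that reported agreement may look lower than in the selected subset, and that the interval will be wide with about 20 patients.
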